9.5.1.3 Response Exploratory Endpoints

Response exploratory endpoints:

- Percentage of participants achieving Investigator's Global Assessment (vIGA) of 0 or 1 with a ≥ 2 Point Improvement from screening.
- Percentage of participants achieving a reduction of ≥ 2 , ≥ 4 in the PP-NRS, of those with a score of ≥ 2 , ≥ 4 at baseline daily from Day 2 to 112.

- Percentage of participants achieving a reduction of ≥ 2 in SD-NRS score, of those with a score of ≥ 2 at baseline daily from Day 2 to 112.

The population summary measure of interest will be the proportion of responders at each timepoint in each treatment group.

The number and percentage of participants who achieve a response will be summarised by timepoint. Exact 95% CIs for the percentage of participants will also be displayed at each timepoint.

Daily PP-NRS and SD-NRS endpoints, will be listed and plotted.

9.5.1.4 Response Subgroup Exploratory Endpoints

For the primary and secondary responder endpoints relating to EASI, IGA and BSA, summaries will be provided comparing the number and percentage of participants in each treatment group who respond at Week 16 between the following subgroups:

- Participants with no rescue therapy use
- Participants with no rescue therapy use after the Week 4 visit
- Participants with no rescue therapy use after the Week 8 visit
- Participants with no rescue therapy use within 4 weeks of the Week 16 visit
- Participants with no rescue therapy use within 2 weeks of the Week 16 visit
- Participants with rescue therapy use within 4 weeks of the Week 16 visit
- Participants with rescue therapy use within 2 weeks of the Week 16 visit

The population summary measure of interest will be the proportion of responders in each subgroup in each treatment group.

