Response (2)	Development of skin infection requiring topical or systemic antibiotic treatment by Week 16	Proportion reporting at least one infection on or before the Week 16 visit.

¹ Evaluated daily from Day 2 to 112.

² Sustained EASI-50 is a response which is seen at least 2 consecutive visits.

³ Sustained PP-NRS or SD-NRS improvement is defined as the relevant improvement shown at all evaluable days within at least a 14-day period.

The primary and selected secondary response endpoints relating to EASI, IGA and PP-NRS endpoints will be used in exploratory estimands which compare those who received topical corticosteroid rescue medication within specific windows with those who used no topical corticosteroid rescue therapy. These estimands will use all data as collected with no imputation for intercurrent events.

For Cohort 4 only, the primary and secondary endpoints relating to EASI, IGA, IGA*BSA and PP-NRS (those endpoints flagged in Table 11-3 for the use of secondary supplementary estimands) will also be used for exploratory estimands which compare the Cohort 1 EDP1815 treatment group with the Cohort 4 EDP1815 treatment group.

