4.1 Study Objectives

The primary objective of the study is:

- To show superiority of EDP1815 over placebo in the proportion of participants achieving at least a 50% reduction in Eczema Area and Severity Index (EASI) score (EASI-50) in the absence of rescue medication for 28 days and in the absence of prohibited medications at any time.

The secondary objectives of the study are:

- To evaluate the clinical benefit of EDP1815 in the treatment of atopic dermatitis.
- To evaluate the safety and tolerability of EDP1815.

The exploratory objectives of the study are:

- To evaluate the time to onset of clinical response to EDP1815.
- To evaluate the most effective dose and dosing frequency of EDP1815 in the treatment of atopic dermatitis.
- To evaluate the effect of EDP1815 on patient reported outcomes.
- To evaluate the effect of early use of rescue therapy on Week 16 responder status.
- To evaluate the relationship of EDP1815 treatment with biomarkers such as immune protein markers, eosinophils, and immune cell RNA profile in blood.
- To evaluate correlation of genetic markers and EDP1815 treatment outcomes.
- To evaluate correlation of gut microbiome and EDP1815 treatment outcomes.

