- Number of days of treatment with TCS/TCI rescue therapy per participant in Weeks 1-4, 5-8, 9-12 and 13-16 and for Weeks 1-16.
- Proportion of participants requiring TCS/TCI rescue therapy in Weeks 1-4, 5-8, 9-12 and 13-16 and for Weeks 1-16.

The secondary safety endpoints for the study are:

- Adverse events and serious adverse events.
- Change from baseline in vital signs.
- Change from baseline in ECG parameters.
- Change from baseline in clinical laboratory parameters.
- Change from baseline in physical examination findings.
- Worst-case change from baseline with respect to potentially clinical important criteria for vital signs, QTcF and clinical laboratory parameters.
- Worst-case change from baseline with respect to values outside the normal ranges for clinical laboratory parameters.

Exploratory endpoints to evaluate the time to onset of clinical response are:

- Time to first achievement of EASI-50.
- Time to first achievement of sustained EASI-50.
- Time to first achievement of EASI-75,
- Time to first achievement of vIGA of 0 or 1 with a 2-point improvement from baseline.
- Time to first achievement of vIGA of 0 or 1.
- Time to first achievement of a ≥ 2 point in improvement in PP-NRS score, in participants with a score of ≥ 2 at baseline.
- Time in days to first sustained ≥ 2 point in improvement in PP-NRS score, in participants with a score of ≥ 2 at baseline.
- Time to first achievement of a ≥ 4 point in improvement in PP-NRS score, in participants with a score of ≥ 4 at baseline.
- Time in days to first sustained ≥ 4 point in improvement in PP-NRS score, in participants with a score of ≥ 4 at baseline.
- Time to first achievement of a ≥ 2 point in improvement in SD-NRS score, in participants with a score of ≥ 2 at baseline.
- Time in days to first sustained ≥ 2 point in improvement in SD-NRS score, in participants with a score of ≥ 2 at baseline.

Exploratory endpoints to evaluate the effect of early use of topical corticosteroid rescue therapy on Week 16 responder status are defined in the following subgroups: the subgroup of participants with no rescue use at any time before Week 16 will be compared to subgroups of participants with rescue therapy use within only the first 4, 8, 12 and 14 weeks of treatment and to participants with rescue therapy use within the 2 weeks and 4 weeks prior to the Week 16 visit. For these subgroups, the following endpoints will be summarized:

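### Four of the seven rescue-use subgroups contain every never-user, so the planned tables understate any difference between early-only rescue users and never-users

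*SAP*

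**What the plan says.** SAP 4.1 lists the exploratory objective: "To evaluate the effect of early use of rescue therapy on Week 16 responder status". SAP 4.2 gives the design of the comparison. The reference is "the subgroup of participants with no rescue use at any time before Week 16", and it is to be compared with "subgroups of participants with rescue therapy use within only the first 4, 8, 12 and 14 weeks of treatment", and also with participants who used rescue in the last 2 or 4 weeks before the Week 16 visit. Protocol 3.4 has the same definition. Protocol 11.3.3 describes the same contrast, saying that these estimands "compare those who received topical corticosteroid rescue medication within specific windows with those who used no topical corticosteroid rescue therapy".

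The analysis sections use a different list. SAP 9.5.1.4 tabulates never-users and then four groups that are defined by what did not happen later:

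- for Week 4: "Participants with no rescue therapy use after the Week 4 visit"
- for Week 8: the same condition, counted from that visit
- for about Week 12: free of rescue during the last 4 weeks up to Week 16
- for about Week 14: free of rescue during the last 2 weeks up to Week 16.

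Two late-use groups, with rescue inside 4 or 2 weeks of Week 16, complete the seven. Protocol 11.4.5 carries the same list, although it announces four subgroups and then names seven.

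The stated summary measure in SAP 9.5.1.4 is the proportion of responders in each subgroup within each treatment group. SAP 9.5.1 assigns these summaries to EDPS7, so data are used as collected. The change table in SAP 13 records no departure from the Protocol 3.4 definition.

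**The concern.** A participant who never used rescue satisfies all four no-later-use conditions. Setting any of these groups beside the never-users compares a group with a larger group that contains it. The percentages are pulled towards each other by construction, and the pull is strongest where early-only users are few.

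The amendment log in the protocol says that the objective was added to help the sponsor assess its estimand approach for Phase 3. The primary estimand takes Week 16 data as collected when the last rescue use was at least 28 days earlier, so whether such participants respond like never-users bears on that choice. A table whose layout favours similar percentages could be taken as more reassurance than it gives. The list feeds seven tables (14.2.1.5, 14.2.2.5, 14.2.3.4, 14.2.7.4, 14.2.8.4, 14.2.14.2 and 14.2.15.2), and the SAP addendum repeats the exploratory analyses for Cohort 4.

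**Working it through.** The plan gives no figure for this summary, so there is none to reproduce.

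**Who is in each group**

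| Group in SAP 9.5.1.4 | Requires any use? | Contains never-users? |
|---|---|---|
| No use at all | No | Is the reference |
| None after Week 4 | No | All |
| None after Week 8 | No | All |
| None within 4 weeks of Week 16 (about Week 12) | No | All |
| None within 2 weeks of Week 16 (about Week 14) | No | All |
| Use within 4 weeks of Week 16 | Yes | None |
| Use within 2 weeks of Week 16 | Yes | None |

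**Attenuation.** Among participants in an arm with Week 16 data, let a be the share of never-users, with response p_N. Let e be the share whose rescue use all fell on or before week k, with response p_E. The planned group has response (a·p_N + e·p_E)/(a + e). Its difference from never-users is

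p_N − (a·p_N + e·p_E)/(a + e) = (p_N − p_E) × e/(a + e).

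The retained share of the true difference is therefore exactly e/(a + e). It is below 100% whenever there are never-users.

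**Size under assumptions.** The documents give no expected rate or timing of rescue. Assume that a proportion t of participants use rescue, each with one course at a uniform time over 16 weeks. Then e = t × k/16 and a = 1 − t. For t = 10% and k = 4: e = 0.025, a = 0.90, and 0.025/0.925 = 2.7%. For t = 70% and k = 14: e = 0.6125, a = 0.30, and 0.6125/0.9125 = 67.1%.

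| Assumed t | Week 4 | Week 8 | Week 12 | Week 14 |
|---|---|---|---|---|
| 10% | 2.7% | 5.3% | 7.7% | 8.9% |
| 20% | 5.9% | 11.1% | 15.8% | 17.9% |
| 40% | 14.3% | 25.0% | 33.3% | 36.8% |
| 60% | 27.3% | 42.9% | 52.9% | 56.8% |
| 70% | 36.8% | 53.8% | 63.6% | 67.1% |

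A Poisson model for repeated courses gives similar or lower values. With 60% ever-users, it gives 20.5%, 36.8%, 49.7% and 55.1%. If all rescue fell in the first 4 weeks, then e = t and the retained share would equal t.

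**In percentage points.** Assume 45% response in never-users and 25% in early-only users, a true gap of 20 points. The displayed gap at Weeks 4, 8, 12 and 14 would be 1.2, 2.2, 3.2 and 3.6 points at t = 20%, and 5.5, 8.6, 10.6 and 11.4 points at t = 60%. With groups that require use, as in SAP 4.2, the displayed gap would be 20 points throughout.

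**The case against.** The best reply is that nothing is lost. The tables show numbers as well as percentages and the groups are nested, so subtracting the never-user counts gives the early-only result exactly. The EDPS7 listings of EASI endpoints (16.2.6.2) and rescue endpoints (16.2.6.12) hold the participant-level data as well. This is correct, and it means that the information is obscured rather than destroyed. It does not repair the planned summary measure, which is the proportion in each listed group.

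A second reply is that the cumulative groups have a use. No rescue within 4 weeks and no rescue within 2 weeks roughly mark the participants whose data escape replacement for rescue under the 28-day rule of EDPS1 and the 14-day rule of EDPS3. Setting them beside never-users shows how far admitting earlier users shifts the response rate. That is a fair question, but not the one that SAP 4.2 poses.

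Third, the rescue rule is tested elsewhere. Supplementary Estimand 2 (14-day window) and Supplementary Estimand 5 (any use counted as non-response) repeat the primary model, so the evaluation of that rule does not rest on these tables. This stands, and it limits the consequence.

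Finally, corrected groups would be small. At an assumed 5% to 15% early-only use, a 75-person arm has about 4 to 11 such participants (75 × 0.05 = 3.75; 75 × 0.15 = 11.25). With 2 responders among 8, the exact 95% interval runs from about 3% to 65%. This also stands.

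**Conclusion.** The inconsistency is real and appears in both documents: SAP 4.2, Protocol 3.4 and Protocol 11.3.3 call for users-only windows, whereas SAP 9.5.1.4 and Protocol 11.4.5 list four groups that include all never-users. The attenuation by early/(never + early) is exact. Its size is not known. Under total rescue use assumed between 10% and 70% with uniform timing, about 3% to 37% of the gap survives in the Week 4 group and about 9% to 67% in the Week 14 group.

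A reader might infer that the effect of early rescue is diluted almost to nothing, or that the tables would show no effect whatever the truth. The documents do not support either reading. Near-disappearance needs low rescue use, about 20% or less, and applies mainly to the Week 4 group. With 40% use or more, one third or more of the gap remains at Weeks 12 and 14. The two late-use groups are not affected, and the counts allow the correct result to be rebuilt.

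The matter is minor. The analysis is exploratory and descriptive, no inference is planned on it, and the primary analysis is untouched.

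**What to change.** In SAP 9.5.1.4, define the four early groups as at least one rescue course on or after Day 1 and none after Week 4, 8, 12 or 14. Show never-users as a separate group and keep the two late-use groups. Align Protocol 11.4.5 with this, with SAP 4.2 and with Protocol 3.4, and correct its count of subgroups. The four early groups will still be nested in one another, as SAP 4.2 intends, but none will overlap with never-users. If the present no-later-use groups are wanted, for example to describe participants whose Week 16 data are taken as collected, they can stay as extra rows with that purpose stated.

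The cost is one flag derivation and a change of wording, with no new data. The downside is small cells. A footnote should say that the comparison conditions on rescue use after randomisation, so it remains a description and not an estimate of the causal effect of early rescue.

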9.5.1.5 Count Exploratory Endpoints

Response exploratory endpoints:

- Number of uses of topical antimicrobial or systemic antibiotic treatment for skin infections by Week 16.

The population summary measure of interest will be the proportion of participants reporting at least one infection on or before the Week 16 visit in each treatment group.

The number and proportion of participants with skin infection requiring topical or systemic antibiotic treatment at least once during the study will be presented. Histogram of the number of courses will be plotted.

10 Safety Analyses

The Safety population will be used for all summaries of Safety. All safety endpoints will be listed.

10.1 Extent of Exposure

The duration of exposure (days) and number of doses taken will be summarized using summary statistics for continuous data. The number and percentage of participants with at least 4, 8, 12 and 16 weeks (28, 56, 84 and 112 days respectively) will also be presented.

Treatment start and stop dates, exposure duration (days), number of doses administered, number of capsules taken and reasons for dose adjustments and dose interruptions will be listed by participant.

10.2 Adverse Events

Adverse events will be reported from the date of signed informed consent and through the Week 16 visit for participants entering the OLE study/28 days after cessation of dosing for participants who don't enter OLE. Adverse events occurring after the 28 days post-treatment would only be reported if the investigator considers it to be related to the study treatment.

Only treatment emergent AEs (TEAEs) will be included in the summaries, pre-treatment AEs will be included in the listings of all AEs.

All AEs will be coded using MedDRA. The dictionary will be updated through the life of the study with version 24.0 used initially. Severity of event will be coded using the Common Terminology Criteria for Adverse Events v5.0 (CTCAE).

An overview of TEAEs will be produced showing the number and percentage of participants with:

- Any TEAEs
- Any TEAE of CTCAE grade 2 or above
- Any TEAE of CTCAE grade 3 or above
- Any TEAE of CTCAE grade 4 or above
- Any fatal TEAE
- Any serious TEAE
- Any TEAE leading to permanent discontinuation of study drug
- Any TEAE leading to withdrawal from the study
- Any related TEAE
- Any related TEAE of CTCAE grade 2 or above
- Any related TEAE of CTCAE grade 3 or above
- Any related TEAE of CTCAE grade 4 or above
- Any related fatal TEAE
- Any related serious TEAE
- Any related TEAE leading to permanent discontinuation of study drug
- Any related TEAE leading to withdrawal from the study

Related events are those which were considered by the investigator to be possibly, probably or definitely related to study drug.

TEAEs will also be summarized by system organ class (SOC) and preferred term (PT). Summary tables will contain the number and percentage of participants and the number of events. A participant who has multiple events in the same SOC or the same preferred term will be counted only once in the participant counts but all events will be counted in the event counts. Adverse event summaries will be sorted by the internationally agreed SOC order ([Table 5](#)) and decreasing incidence of preferred term within SOC in the EDP1815 column.

Related TEAEs and TEAEs of CTCAE Grade 3 or above will also be summarized by SOC and PT in the same manner as described above.

Non-serious TEAEs will be also summarised by SOC and PT, however, PTs will be presented only in case of TEAEs reported by at least 5% of participants in any treatment group.

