The severity and frequency of Adverse Events will be used to evaluate the safety and tolerability of EDP1815.

Exploratory endpoints: A number of exploratory endpoints will be evaluated to determine further aspects of treatment efficacy including time to achieve clinical response and patient reported health outcomes. Changes in eosinophils, immune protein markers and immune cell RNA profile will be used to evaluate the effect of EDP1815 treatment on biomarkers in blood. A fecal sample will be used for microbiome profiling. Human Leukocyte Antigen (HLA) typing will be performed in those participants who consent to assess the correlation with clinical outcomes.

Brief Study Design: This study will evaluate EDP1815 in participants with mild, moderate, and severe atopic dermatitis, to compare efficacy, safety, and tolerability to placebo. The Investigational Medicinal Product (IMP) is EDP1815 or matching placebo. The study will be blinded to the participants, Investigator, and Sponsor.

Approximately 405 participants will be randomized to receive either EDP1815 or placebo (295 to EDP1815: 110 to placebo) and treated for 16 weeks. Following end-of-treatment assessments, participants may enter a 4-week post-treatment follow-up period or may elect to participate in an Open Label Extension (OLE) Protocol for EDP1815, if available. Cohorts 1, 2 & 3 will be run concurrently, and Cohort 4 recruitment will commence after enrollment for Cohorts 1, 2, & 3 are completed.

Participants will be dosed with EDP1815 or matching placebo administered as the following:

- **Cohort 1:** 1.6×10^{11} total cells of EDP1815 or matching placebo administered as 2 capsules once daily.
- **Cohort 2:** 6.4×10^{11} total cells of EDP1815 or matching placebo administered as 2 capsules once daily.
- **Cohort 3:** 6.4×10^{11} total cells of EDP1815 or matching placebo administered as 1 capsule of 3.2×10^{11} cells twice daily.
- **Cohort 4:** 8.0×10^{10} total cells of EDP1815 or matching placebo administered as 1 capsule once daily.

Participants in Cohorts 1, 2, & 3 will be randomized in a 3:1 ratio (225 to EDP1815: 75 to placebo). Participants in Cohort 4 will be randomized in a 2:1 ratio (70 to EDP1815: 35 to placebo). Randomization to Cohort 4 will not start before randomization to Cohorts 1, 2 & 3 have completed.

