11.3.4. Safety Estimands

All safety estimands will use the safety analysis set. A treatment policy approach will be used for all safety estimands, including all data collected regardless of treatment discontinuation, treatment compliance, changes in background or rescue therapy or unblinding of the subject.

SDPS1 will be used to estimate safety endpoints which are collected at scheduled visits.

SDPS2 will be used to estimate safety endpoints which are assessed at any time in the study.

Table 11-4: Safety Endpoint Details

Data Point Set	Endpoint	Population Summary Measure of Interest
SDPS1	Change from baseline in vital signs Change from baseline in ECG parameters Change from baseline in clinical laboratory parameters Change from baseline in physical examination findings	Summary statistics at each visit for each treatment group
SDPS2	Adverse events and serious adverse events Worst-case change from baseline with respect to potentially clinical important criteria for vital signs, QTcF and clinical laboratory parameters Worst-case change from baseline with respect to values outside the normal ranges for vital signs, ECG parameters and clinical laboratory parameters	Incidence in each treatment group

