5.1 General Study Design and Plan

This is a randomised, double-blind, placebo-controlled study to evaluate the efficacy, safety and tolerability of EDP1815 as compared to placebo in participants with mild, moderate and severe atopic dermatitis.

Cohorts 1, 2 & 3 will be run concurrently, and Cohort 4 recruitment will commence after enrollment for Cohorts 1, 2, & 3 are completed. During the Cohorts 1, 2, & 3 enrolment after eligibility is confirmed during the screening period ([Protocol Sections 5.1 and 5.2](#)), participants will be randomly assigned in a 1:1:1 ratio to 1 of the cohorts 1, 2 or 3. Once recruitment to first three cohorts is completed all participants will enrol cohort 4:

[figure not shown]
- **Cohort 1:** 1.6×10^{11} total cells of EDP1815 or matching placebo administered as 2 capsules once daily.
- **Cohort 2:** 6.4×10^{11} total cells of EDP1815 or matching placebo administered as 2 capsules once daily.
- **Cohort 3:** 6.4×10^{11} total cells of EDP1815 or matching placebo administered as 1 capsule of 3.2×10^{11} cells twice daily.
- **Cohort 4:** 8.0×10^{10} total cells of EDP1815 or matching placebo administered as 1 capsule once daily.

Participants in Cohorts 1, 2, & 3 will be randomised in a 3:1 ratio (approximately 75 to EDP1815 and 25 to placebo within each cohort, 300 in total). Participants in Cohort 4 will be randomised in a 2:1

ratio (approximately 70 to EDP1815: 35 to placebo, 105 in total). So approximately 405 participants will be randomised in total.

As shown in Figure 1, the study comprises a screening period of up to 4 weeks, a treatment period of 16 weeks, and a 4-week post-treatment follow-up period, which results in a maximum study duration of up to 24 weeks. Should a participant elect to participate in an Open Label Extension (OLE) protocol for EDP1815, the follow-up period will be skipped, and the study duration would be a maximum of 20 weeks.

Figure 1 Study Schema

An interim analysis may be undertaken prior to the end of recruitment in cohorts 1-3. The purpose of this interim analysis is to check that the treatment groups have remained balanced and that the use of stratified randomisation has not led to issues caused by multiple incomplete blocks of randomisation. A separate interim analysis process plan is available which provides all relevant details.

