5.3.4.2 Treatment-Emergent Adverse Events

An adverse event (AE) will be classified as ‘treatment-emergent’ if the onset date/time was on or after the start date/time of study treatment. Where dates or times are missing or partially missing, AEs will be assumed to be treatment-emergent, unless there is clear evidence (through comparison of partial dates/times, see [Section 7.3.1](#)) to suggest that the AE started prior to dosing.

AEs will be classified into the following study phases based on the onset date/time of the AE after any imputations:

- Pre-Treatment Phase: All AEs with onset date/time prior to the first dose of randomised study treatment
- Treatment Phase: All AEs with onset date/time at the time of or after the first dose of randomised study treatment (Day 1) up to and including the date of the last dose of treatment received.
- Follow-up Phase: All AEs with onset date after the date of the last dose of treatment received.

For participants who complete 16 weeks of dosing per protocol, the Treatment Phase will be from Day 1 to the Week 16 visit, and the Follow-up Phase will start after the Treatment Phase and last until their last day in the study. In all cases the day will be assumed to start at 00:00 hours and end at 23:59 hours. Adverse events occurring in both the Treatment Phase and Follow-up Phase are classified as treatment emergent.

The onset phase of all AEs will be included in the relevant data listings.

6 Sample Size

Cohorts 1-3

The sample size was calculated using the assumption that data from the placebo participants in the three cohorts can be pooled prior to comparison with the EDP1815 treatment groups. No adjustments for multiple testing have been made.

The primary efficacy endpoint is the achievement of EASI-50 at Week 16. The pooled placebo response rate is estimated to be approximately 25% and a doubling of this to 50% for EDP1815 would be considered as clinically meaningful.

Using a two-sided test at the 5% level of significance, 58 participants in each treatment group would give 80% power to detect a difference in one of the EDP1815 cohorts compared to the pooled placebo group. There would also be more than 90% power to compare the pooled EDP1815 group to the pooled placebo group.

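### Among participants who complete treatment, the TEAE tables cover 16 weeks for those who enter the open-label extension and about 20 weeks for those who do not, with no output that separates or adjusts for the two windows

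*SAP*

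**What the plan says.** - **Reporting window.** SAP 10.2 reports adverse events from consent "through the Week 16 visit for participants entering the OLE study/28 days after cessation of dosing" for those who do not enter it. After 28 days post-treatment, only events judged related are reported.
- **Definition.** SAP 5.3.4.2: "Adverse events occurring in both the Treatment Phase and Follow-up Phase are classified as treatment emergent". For participants who complete dosing, the Treatment Phase ends at the Week 16 visit. For others it ends at the last dose.
- **Use of phase.** SAP 5.3.4.2: "The onset phase of all AEs will be included in the relevant data listings". No summary table by phase is specified, and the safety table list in SAP 15.3.1 has none.
- **Measure.** SAP 10.2: "Summary tables will contain the number and percentage of participants and the number of events". Protocol Table 11-4 names the measure as "Incidence in each treatment group". SAP 10.1 summarises time on treatment, not time under adverse event observation.
- **Entry to the extension.** In the Protocol Summary, participants "may elect to participate in an Open Label Extension (OLE) Protocol for EDP1815, if available". Protocol 7.7 restricts entry to those who complete all 16 weeks of study product.
- **Columns.** SAP Section 8 sets one All Placebo column beside each cohort's EDP1815 column and an All EDP1815 column. No Cohort 4 placebo column is listed for safety, so All Placebo appears to pool all four cohorts in the final analysis.

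**The concern.** Among completers, the length of observation depends on a choice made after randomisation, and response or tolerability may influence that choice. It may also depend on calendar time: Cohort 4 starts only after Cohorts 1-3 have enrolled (Protocol 4.1), and the extension is offered only where it exists. A crude percentage treats 16 and 20 weeks of observation alike, so columns with different extension uptake could show different incidence when the drug does nothing.

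Safety and tolerability is a secondary objective, and these tables are its main evidence. Three of them are marked for the top-level results. The non-serious TEAE table shows preferred terms only at 5% or more in any group, so window length alone could decide whether a term near that threshold appears.

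**Working it through.** **Windows.** SAP 5.1 gives a duration for non-entrants, "which results in a maximum study duration of up to 24 weeks", and 20 weeks for entrants. Both reproduce: 4 + 16 + 4 = 24 and 4 + 16 = 20. Without screening, the post-dose windows are 16 weeks (112 days) for entrants and 112 + 28 = 140 days, or 20 weeks, for completers who do not enter. That is 20/16 = 1.25, or 25% more observation time.

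**Assumptions.** The documents give no adverse event rates and no extension uptake. I assume a constant hazard, no drug effect, and incidence p16 at 16 weeks. Then p20 = 1 − (1 − p16)^(20/16).

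| p16 | p20 | Gap |
|---|---|---|
| 30% | 36.0% | 6.0 points |
| 45% | 52.6% | 7.6 points |
| 60% | 68.2% | 8.2 points |

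With uptake u, a column shows u × p16 + (1 − u) × p20.

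**Uptake differing by arm, p16 = 45%.**
- 80% uptake: 0.8 × 45 + 0.2 × 52.6 = 46.5%.
- 60% uptake: 0.6 × 45 + 0.4 × 52.6 = 48.1%.
- Difference: 0.2 × 7.64 = 1.5 points.

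These levels give every non-entrant 20 weeks, which is wrong for early discontinuers. Protocol 11.8 assumes 20% drop-out before Week 16. If 80% and 60% are uptake among completers, and early discontinuers contribute equally to both columns, the difference is 0.8 × 1.5 = 1.2 points.

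**Extension absent in Cohort 4, 80% uptake in Cohorts 1-3, p16 = 45%.**
- Cohort 4 EDP1815: 52.6%.
- Each Cohort 1-3 EDP1815 column: 46.5%.
- All Placebo, with 75 from Cohorts 1-3 and 35 from Cohort 4: (75 × 46.5 + 35 × 52.6)/110 = 48.5%.
- Cohort 4 EDP1815 minus All Placebo: (75/110) × 0.8 × 7.64 = 4.2 points. If 80% is uptake among completers, 0.8 × 4.2 = 3.3 points.
- Each of Cohorts 1-3 minus All Placebo: −(35/110) × 0.8 × 7.64 = −1.9 points.

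**Equal uptake in every column.** The mixture is the same everywhere and the artefact is 0.

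**The 5% display threshold.** A preferred term at 4.5% over 16 weeks becomes 1 − 0.955^1.25 = 5.6% over 20 weeks.

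**The case against.** Within a cohort, treatment is blinded and the reporting rule is the same for both arms, so bias there needs uptake to differ by arm. Nothing in the documents says that it will, and the direction could go either way. The arm-related artefact of 1.2 to 1.5 points is small beside sampling error: for 75 versus 110 participants at 48%, the standard error is √(0.48 × 0.52 × (1/75 + 1/110)) = 7.5 points. Safety is summarised, not tested. The Cohorts 1-3 analysis (SAP 7.4.3) includes only those cohorts, so three of the four active groups also get a comparison with concurrent placebo. Keeping a 28-day post-dose window, and ending this study's reporting when a participant moves to another EDP1815 protocol, is a defensible convention. All of this stands and limits the importance of the point. It does not remove the unequal windows or the absence of any output that would reveal their effect.

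A reader might go further in four ways that the documents do not support.

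- **All non-entrants are observed for 20 weeks.** Only completers are. An early discontinuer has time on treatment plus 28 days, which can be less than 16 weeks.
- **The cross-stage artefact against placebo is 6.1 points** (52.6% − 46.5%). That is Cohort 4 EDP1815 against a Cohort 1-3 EDP1815 column. The pooled placebo column contains Cohort 4 participants, which reduces the gap.
- **Every TEAE table is inflated.** Among completers, an event starting after the final dose cannot lead to discontinuation of study drug, so that table is unaffected.
- **The main tables should move to Treatment Phase onset.** That phase ends at last dose for early discontinuers, so it is not a window common to all. The change would also take events that start just after stopping drug out of the main serious, related and grade 3+ displays.

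**Conclusion.** The point holds in a limited form. The plan mixes two observation windows among completers, set by an elective step after randomisation that may also vary by stage of the trial, and reports crude incidence without showing the split. The possible distortion is about 1.2 to 1.5 points for 80% versus 60% uptake. It is about 3.3 to 4.2 points for Cohort 4 EDP1815 against pooled placebo if the extension is absent in Cohort 4 and taken up by 80% in Cohorts 1-3. These figures rest on an assumed 45% incidence at 16 weeks, a hazard that stays constant through four weeks off drug, assumed uptake, and the reading that All Placebo pools all four cohorts. Under equal uptake the distortion is zero. The documents do not show that a safety signal is being masked or created, only that the planned outputs could not rule it out. The primary endpoint is untouched. Severity: consider.

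**What to change.** Keep all planned TEAE tables and add the following.

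1. A TEAE overview and a SOC/PT summary restricted to onset from Day 1 through the Week 16 visit. For early discontinuers, count onset through last dose plus 28 days, capped at the Week 16 target day (Day 113 in protocol Table 4-1). This removes the dependence on extension entry among completers without assuming a constant hazard, and keeps events that start soon after an early stop, up to the cap. Alternatively, give rates per person-time of adverse event observation. The denominator must not be the treatment exposure in SAP 10.1, because follow-up events would then enter the numerator without their time in the denominator.
2. A table of Follow-up Phase events, with participants who entered follow-up as the denominator.

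The cost is a few extra tables built from dates and a phase variable that the SAP already derives. No new data are needed and no event leaves the existing displays. Specifying these tables before Cohort 4 is unblinded avoids a later choice of window.
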